ICH E6	International Conference on Harmonisation Guidance for Industry, Good Clinical Practice:
	Consolidated Guidance
ICMJE	International Committee of Medical Journal Editors
IDE	Investigational Device Exemption
IND	Investigational New Drug Application
IRB	Investigational Review Board
ISO	International Organization for Standardization
LSMEANS	Least Squares Means
MedDRA	Medical Dictionary for Regulatory Activities
MOP	Manual of Procedures
MSDS	Material Safety Data Sheet
NIH	National Institutes of Health
NIH IC	NIH Institute & Center
OHRP	Office for Human Research Protections
PI	Principal Investigator
QA	Quality Assurance
QC	Quality Control
SAE	Serious Adverse Event
SAP	Statistical Analysis Plan
SMC	Safety Monitoring Committee
SOC	System Organ Class
SOP	Standard Operating Procedure
LID	Unanticipated Dyahlam
UP	Unanticipated Problem

STATEMENT OF COMPLIANCE

The trial will be conducted in accordance with the ICH E6, the Code of Federal Regulations on the Protection of Human Subjects (45 CFR Part 46), and the <NIH IC> Terms of Award. The Principal Investigator will assure that no deviation from, or changes to the protocol will take place without prior agreement from the sponsor and documented approval from the Institutional Review Board, except where necessary to eliminate an immediate hazard(s) to the trial participants. All personnel involved in the conduct of this study have completed Human Subjects Protection Training.

I agree to ensure that all staff members involved in the conduct of this study are informed of their obligation to meet the above commitments.

Principal Investigator:	- Print/Type Name		
Signed:		Date:	

PROTOCOL SUMMARY

A Phase II Biomarker Trial of CC-122 in Combination with Nivolumab in Advanced Melanoma

Précis:

Preliminary pre-clinical data suggest that the novel immunomodulatory agent CC-122 can restore metabolic function of T-cells and will increase immunosurveillance in melanoma. The synergy of the combination of CC-122 and the anti-PD1 agent nivolumab will enhance reversal of T-cell exhaustion and improve anti-tumor immunity in patients with advanced melanoma. Our goal is to link pharmacodynamic markers to immune mechanism of action and efficacy. In addition, we seek to define sub-populations that may be enriched for response to CC-122 plus nivolumab in melanoma.

Objectives:

Primary: To determine the response rate to combination CC-122 plus nivolumab in both anti-PD1 naïve and anti-PD1 refractory advanced melanoma.

Secondary: (1) To assess the toxicity of this combination. (2) To determine the progression-free survival and overall survival with this combination. (3) Examine blood and tissue-based biomarkers that will further our understanding of the complex interplay between the metabolic needs/changes in the tumor and the immune microenvironment.

Population:

Adults with advanced melanoma who are appropriate for treatment with anti-PD1 therapy or who are appropriate to resume anti-PD1 therapy after prior progression on anti-PD1 therapy with the goal of reversing resistance.

Number of Sites

This study will be conducted at the Moffitt Cancer Center

Study Agent(s) and Administration:

Oral CC-122 at 2mg daily for 5 consecutive days every 7 days, with intravenous nivolumab (240mg) in days 1 and 15 within a 28-day cycle.

[figure not shown]
Study Duration:

Subjects will receive up to 52 weeks of therapy. Decision to continue beyond this will be made based on response at that time. Based on planned futility analyses and enrollment across cohorts, the total number of subjects is anticipated to be 44-66.

Participant Duration:

Participants to be followed for up to 24 months following completion of study therapy.

SCHEMATIC OF STUDY DESIGN

KEY ROLES

2 INTRODUCTION: BACKGROUND INFORMATION AND SCIENTIFIC RATIONALE

2.1 BACKGROUND INFORMATION

The advent of immune checkpoint inhibitors against cytotoxic T-lymphocyte antigen-4 (CTLA-4) and programmed death 1 (PD-1), as well as mitogen activated protein kinase (MAPK) targeted therapy has revolutionized the management of advanced melanoma, a disease long associated with therapeutic futility and nihilism. The median survival for patients with metastatic disease treated with a first-line regimen that includes an inhibitor of PD-1 has now approached 36 months, with 3-year overall survival (OS) in excess of 50%. Since 2011, eight new drugs have received regulatory approval in the United States either as single agents or in combination. These include the immune checkpoint inhibitors ipilimumab, nivolumab, and pembrolizumab, MAPK targeting agents including vemurafenib, dabrafenib, cobimetinib, and trametinib, and finally intra-lesional oncolytic virotherapy talimogene laherparepvec (T-VEC). While cure may be a distinct possibility for some patients with stage IV melanoma, there are nonetheless 10,000 melanoma deaths annually in the United States. This clearly underscores the ongoing need for further enhancement in melanoma therapeutics.

The PD-1 blocking antibodies, pembrolizumab and nivolumab elicit objective response rates (ORR) between 30% and 40% in metastatic melanoma, with complete response (CR) rates ranging from 5% to 8%.34 In KEYNOTE-001, pembrolizumab was administered at 10 mg/kg every 2 weeks, 10 mg/kg every 3 weeks, or 2 mg/kg every 3 weeks and included both ipilimumab-treated and ipilimumab-naïve metastatic melanoma patients.⁵ In a pooled analysis, the ORR was 33% with median OS of 23 months; for therapynaïve patients these were 45% and 31 months respectively. In KEYNOTE-006, pembrolizumab improved the ORR, progression-free survival (PFS), and overall survival (OS) compared with ipilimumab in advanced melanoma.³ Remarkably similar results for efficacy and toxicity have been observed with nivolumab as well.^{4,6} In CheckMate-067, previously untreated advanced melanoma patients were randomized to receive combination nivolumab plus ipilimumab (followed by maintenance nivolumab), nivolumab alone, or ipilimumab alone. The response rates to treatment were 58%, 44% and 19% respectively. Both nivolumabcontaining arms improved OS compared to ipilimumab. At 3 years, the OS rate was 58%, 52%, and 34% respectively in these cohorts. The toxicity of combination nivolumab plus ipilimumab can be severe and prohibitive. In CheckMate-067, the rate of grade 3 and 4 adverse events to combination therapy was 59% and the rate of treatment discontinuation secondary to toxicity was 30% compared to 8% on nivolumab alone. Similarly, in KEYNOTE-029, low-dose ipilimumab was combined with standard-dose pembrolizumab in a phase 1b trial that enrolled 153 patients. The ORR to the combination was 61% with one year PFS and OS of 69% and 89% respectively. Overall, 45% patients experienced grade 3 and 4 adverse events and 14% had to discontinue pembrolizumab and ipilumumab due to toxicity. In the absence of proven survival benefit for combination anti-PD1 plus anti-CTLA-4 immunotherapy compared to anti-PD1 therapy alone, single agent anti-PD1 therapy using pembrolizumab or nivolumab remain an appropriate standard of care for metastatic or unresectable melanoma as first-line therapy. This is endorsed as a category 1

recommendation in the NCCN guidelines (Version 2.2018). In addition, this is an appropriate option after progression (or plateau of response) on combination mitogen activating protein kinase (MAPK)-directed treatment for those patients whose tumors harbor a mutation in *BRAF* V600.

In ongoing research efforts in melanoma, important questions being addressed include optimizing the response to first-line anti-PD1 therapy as well as identifying mechanisms to abrogate the development of resistance to anti-PD1 therapy. Similarly the optimal duration of anti-PD1 therapy stratified by response has yet to be refined, as studies of anti-PD1 therapy in melanoma have generally continued treatment until the development of disease progression, unacceptable toxicity, up to 24 months, or even without a prespecified end-date to treatment in cases of perceived therapeutic benefit. Several agents targeting the tumor or the microenvironment are currently under investigation aiming to add to the known efficacy of pembrolizumab or nivolumab in melanoma. Some of these include targeting other checkpoint pathways (TIM3, LAG3, CD137, GITR, etc.) or molecular targets (BRAF, MEK, IDO, HDAC, VEGF).

Approximately 40-45% of cutaneous melanomas harbor an oncogenic mutation in *BRAF* resulting in constitutive activation of the MAPK pathway. In independent phase III trials, combination therapy with a BRAF inhibitor and MEK inhibitor has been shown to improve survival compared to a BRAF inhibitor alone. ^{9,10-12} The combinations of dabrafenib and trametinib, or vemurafenib and cobimetinib are now approved in the management of advanced *BRAF*-mutated melanoma. While these combinations have a high response rate, resistance is invariable and the median time to progression is typically between 10 and 12 months. Current therapeutic strategies are examining the combination of MAPK-targeted therapy with checkpoint inhibition, though these are in the early stages of conduct.

The demonstrable efficacy of cellular immunotherapies, including checkpoint blockade, Tumor Infiltrating Lymphocyte (TIL) therapy, Chimeric Antigen Receptor (CAR)-T cells ¹³⁻¹⁵ and other immune modulators have drastically altered the landscape of cancer therapeutics. There is, however, an urgent need to further delineate mechanisms associated with immune suppression, and to identify targetable pathways that control the intratumoral activity of antigen-specific T-cells. Virtually all of these therapeutic T-cell modalities face potential inactivation after entering the hostile environment of solid tumors, where nutrient and oxygen depletion decreases their migration to the cancer site and reduces their cytotoxic potential in the tumor bed. Overcoming the functional limitations caused by microenvironment-induced restrictions may potentially improve all types of T-cell-related immunotherapies including responses to checkpoint blockade.

2.2 RATIONALE

Immunomodulatory drugs (IMiDs) like thalidomide and lenalidomide, which have proven efficacy in hematological malignancies including multiple myeloma, non-Hodgkin's lymphoma and myelodysplastic syndrome have had limited success in solid tumors including melanoma. In a phase II trial in melanoma, thalidomide demonstrated no objective response and one stable disease in 14 treated patients. In a separate phase II trial, 7/20 (35%) melanoma patients experienced stable disease for a median of 16 weeks. Reported toxicity was as anticipated including constipation, somnolence, fatigue and xerosis. This initial enthusiasm for thalidomide as an effective drug in melanoma due to its biologic modulatory and anti-angiogenic effects rapidly led to its incorporation into combination therapy trials with chemotherapy or other biologic agents. In a small dose-finding trial, the combination of thalidomide and temozolamide was shown to be tolerable and active. In a follow-up study of 38 patients with advanced melanoma, twelve experienced an objective response (32%), including one with a complete response. The median overall survival was 9.5 months. However a larger phase 2 multi-center trial (Southwest Oncology Group 0508) in 64 patients failed to confirm this efficacy yielding a response rate of 13%, 6-month PFS of 15%,

and 1-year overall survival of 35%.20

Based on pre-clinical and phase 1 clinical study data, lenalidomide has also been examined as a single agent in metastatic melanoma. In a large randomized, double-blind phase 2/3 study, 294 patients were randomized to receive oral lenalidomide at 5mg or 25mg daily. There was no significant difference between the response rates (3.4% versus 5.5% respectively), PFS or OS between the two groups. Myelosuppression was observed in 37% of patients. Similarly a parallel study comparing lenalidomide (25mg/d, days 1-21 in a 28-day cycle) to placebo in 306 previously treated melanoma patients demonstrated no difference in the response rate, time to progression or OS between the two arms. The authors concluded limited efficacy of this single agent, but suggested further investigation as a part of combination therapy in melanoma. Separate studies of combination of lenalidomide with sorafenib, valproic acid and bevacizumab have been shown to be safe with evidence of clinical benefit in melanoma among other solid tumors. ²³⁻²⁵

Pre-clinical data suggests synergy between immune checkpoint inhibitors and iMiDs. In a phase 1 trial, ipilimumab at escalating doses (1.5-3mg/kg iv every 3 weeks X 4 doses) was combined with lenalidomide (10-25mg daily for 21 of 28 days) in 36 patients. The maximum tolerated dose was not reached and ipilimumab at 3mg/kg (every 3 weeks X 4) plus lenalidomide at 25mg daily (21/28 days) was identified as the recommended phase 2 dose. Grade 3 rash and grade 3 pancreatitis were identified as dose-limiting toxicities and 8 patients experienced tumor shrinkage ranging from -79% to -2% based on immune-related response criteria (iRECIST).

[figure not shown]

[figure not shown]

Hypothesis:

Summary Statement: The synergy of the combination will enhance reversal of T-cell exhaustion and improve anti-tumor immunity.

We hypothesize that Avadomide (CC-122; Celgene Corporation) will increase immunosurveillance and clinical efficacy in combination with anti-PD1 immunotherapy. Enhanced polyamines suppress aging in vertebrate species and increase the survival of long-lived memory T-cells. Thus, the ultimate test of this hypothesis is to administer CC-122, a potent IMiD, in combination with anti-PD1 in vivo.

3 OBJECTIVES AND PURPOSE

The primary objective of this study is to determine the efficacy and toxicity of the combination of CC-122 and nivolumab in advanced melanoma. Extensive biomarker analyses are planned to obtain a better understanding of the metabolic and immune changes that occur with this combination.

Primary Objective:

 To determine the response rate of the combination of CC-122 plus nivolumab in advanced melanoma as measured by RECIST v1.1.

Secondary Objectives:

- 1. To assess the toxicity of this combination.
- 2. To determine the iRECIST response, progression-free survival and overall survival with this combination.
- 3. Examine blood and tissue-based biomarkers that will further our understanding of the complex interplay between the metabolic needs/changes in the tumor and the immune microenvironment.
 - To determine if clinical improvement is associated with c-Myc induction, glucose uptake, polyamine production, and T-cell persistence.

4 STUDY DESIGN AND ENDPOINTS

4.1 DESCRIPTION OF THE STUDY DESIGN

This is a single-center, open label phase II clinical trial examining the combination of CC-122 plus nivolumab in anti-PD1 therapy naïve or refractory advanced melanoma.

4.2 STUDY ENDPOINTS

The primary end-point is to determine the objective response rate of the combination of CC-122 plus nivolumab in both anti-PD1 therapy naïve advanced melanoma as well as in anti-PD1 therapy refractory melanoma (primary refractory or progressing after an initial response or stable disease). Survival analyses will be conducted. A strong component of this clinical trial is collection of biological specimens to assess pharmacodynamics markers of response to CC-122 and nivolumab and to explore immunometabolic changes that occur in the tumor, microenvironment and blood with this therapy. This may help inform further immune checkpoint pathways/molecules in cancer as well as enable understanding of mechanisms of resistance to anti-PD1 therapy.

STUDY ENROLLMENT AND WITHDRAWAL

5.1 PARTICIPANT INCLUSION CRITERIA

5

The participating subject must meet all of the following inclusion criteria to be eligible to enroll in this study.

- Unresectable or metastatic melanoma of cutaneous, mucosal, conjunctival, or unknown origin.
 Uveal melanoma is not permitted.
 - A. Cohort 1: Naïve to anti-PD1 therapy
 - B. Cohort 2: Progressed on previous anti-PD1 therapy. Subjects who have received anti-PD1 therapy in the adjuvant setting for previously resected melanoma are eligible for this cohort provided the disease relapse has occurred within 6 months of the last dose of anti-PD1 therapy. If this interval is equal to or greater than 6 months from the last dose of anti-PD1 therapy, they will be eligible to participate in Cohort 1. Patients with BRAF V600 mutant melanoma who have PD-1 refractory disease must have received treatment with BRAF and/or MEK inhibitors.
- 2. Be willing and able to provide written informed consent for the trial.
- 3. Be >/=18 years of age on day of signing informed consent.
- 4. Have measurable disease based on RECIST 1.1.43
- 5. Have a performance status of 0 or 1 on the ECOG Performance Scale.
- 6. Female subject of childbearing potential should have a negative urine or serum pregnancy within 72 hours prior to receiving the first dose of study medication. If the urine test is positive or cannot be confirmed as negative, a serum pregnancy test will be required.
- 7. Female subjects of childbearing potential should be willing to use 2 methods of birth control or be surgically sterile, or abstain from heterosexual activity for the course of the study through 28 days after last dose of avadomide or 5 months after the last dose of nivolumab; whichever is longer. Females of childbearing potential are those who have not been surgically sterilized or have not been free from menses for > 1 year.
- 8. Male subjects should agree to use an adequate method of contraception starting with the first dose of study therapy through3 months after the last dose of avadomide or 7 months after last dose of nivolumab; whichever is longer.
- 9. Demonstrate adequate organ function as defined below:
 - Absolute Neutrophil Count (ANC) ≥ 1.5 x 10⁹/L
 - Platelets ≥ 100,000 x 10⁶/L
 - Hemoglobin (Hgb) ≥ 9 g/dL, without the need for transfusion
 - Serum creatinine ≤ 1.5 x institutional upper limit of normal (ULN) OR measured creatinine clearance ≥ 60 mL/min for subject with creatinine levels > 1.5 X institutional ULN
 - Serum AST and ALT $\leq 2.5 \times ULN$ (or $\leq 5 \times ULN$ in case of liver metastases)
 - Serum bilirubin \leq 1.5 x ULN (or \leq 3 X ULN if known Gilbert's syndrome)

5.2 PARTICIPANT EXCLUSION CRITERIA

The subject must be excluded from participating in the trial if the subject:

- 1. Has received an investigational drug or other anti-cancer therapy within 3 weeks of the first dose of treatment or ≤ 5 half-lives of that agent, whichever is shorter. Any toxicity from prior therapy must have recovered to ≤ grade 1.
- 2. Has a diagnosis of immunodeficiency or is receiving systemic steroid therapy (equivalent to > 10mg/d of prednisone) or any other form of immunosuppressive therapy within 7 days prior to

- the first dose of trial treatment (only exception to this is the need for steroids for CNS metastases; see #6 below). Inhaled, intra-articular, or topical steroids are permissible.
- 3. Has a history of hypersensitivity to nivolumab.
- 4. Has a known additional malignancy that is progressing or requires active treatment, the lack of which would pose a risk to the health of the subject, in the opinion of the investigator.
- 5. Has known symptomatic central nervous system (CNS) metastases and/or carcinomatous meningitis. Subjects with previously treated brain metastases may participate provided they are stable without evidence of progression by imaging for at least four weeks after definitive intervention and using no more than the equivalent of dexamethasone 2mg/d for the management of vasogenic edema, if necessary. This exception does not include carcinomatous meningitis, which is excluded regardless of clinical stability.
- 6. Has active autoimmune disease that has required systemic treatment in the past 2 years (i.e. with use of disease modifying agents, corticosteroids or immunosuppressive drugs). Replacement therapy (e.g., thyroxine, insulin, or physiologic corticosteroid replacement therapy [</= 10 mg/d equivalent of prednisone] for adrenal or pituitary insufficiency, etc.) is not considered a form of systemic treatment.

- 7. Had previous toxicity from anti-PD1/PD-L1 immunotherapy that led to treatment discontinuation.
- 8. Has active pneumonitis or a history of non-infectious pneumonitis that required steroids.
- 9. Has grade ≥ 2 peripheral neuropathy.
- 10. Has clinically significant cardiac disease including any of the following: Left ventricular ejection fraction (LVEF) < 45% as determined by a by multi-gated acquisition (MUGA) scan or echocardiogram (ECHO), complete left bundle branch or bifascicular block, congenital long QT syndrome, persistent or clinically meaningful ventricular arrhythmias, QTcF > 460 msec on screening electrocardiogram (ECG), unstable angina pectoris or myocardial infarction ≤ 6 months prior to starting study treatment, uncontrolled hypertension (blood pressure > 140/90 mmHg on at least 2 measurements on sequential visits, despite blood pressure medication), or troponin-T/I value > ULN or brain natriuretic peptide (BNP) > 300 pg/mL
- 11. Has a history of persistent skin rash
- 12. Has an active infection requiring systemic therapy.
- 13. Has known psychiatric or substance abuse disorders that would interfere with cooperation with the requirements of the trial, in the opinion of the investigator.
- 14. Is pregnant or breastfeeding.
- 15. Has a known history of Human Immunodeficiency Virus (HIV), active Hepatitis B (e.g., HBsAg reactive) or Hepatitis C (e.g., HCV RNA is detected).
- 16. Has received a live vaccine within 30 days of planned start of study therapy.

 Note: Seasonal influenza vaccines for injection are generally inactivated flu vaccines and are allowed; however intranasal influenza vaccines (e.g., Flu-Mist®) are live attenuated vaccines, and are not allowed.

It should be noted that screening of a potential subject may proceed after appropriate informed consent has been obtained even if all inclusion/exclusion criteria are not met at the time of signing the ICF.

5.3 STRATEGIES FOR RECRUITMENT AND RETENTION

This trial will be open to all potential subjects who meet eligibility criteria, including women and minorities. Participants considered vulnerable (children, pregnant women, incarcerated, mentally ill, incapable of informed consent) will not be enrolled in this study. Subjects will be identified through the multi-disciplinary Cutaneous Oncology clinic at the Moffitt Cancer Center.

5.4 PARTICIPANT WITHDRAWAL OR TERMINATION

Participants may withdraw voluntarily from the study or the PI may terminate a participant from the study.

5.4.1 REASONS FOR WITHDRAWAL OR TERMINATION

Participants are free to withdraw from participation in the study at any time upon request. An investigator may terminate participation in the study in the following circumstances:

- If any clinically adverse event (AE), laboratory abnormality, or other medical condition or situation occurs such that continued participation in the study would not be in the best interests of the participant
- If the participant meets an exclusion criterion (either newly developed or not previously recognized) that precludes further study participation.
- Any subject who becomes pregnant during the study, must be promptly withdrawn from the study and
 discontinue further study treatment. All subjects and female partners of male subjects who become
 pregnant must be followed to the completion/termination of the pregnancy. This is discussed in additional
 detail in section 8.4.5 along with the required reporting guidelines.

If the subject is agreeable, all efforts will be made to continue follow-up of withdrawn or terminated participants, especially for safety and efficacy end-points. All protocol specific safety follow-up procedures to capture adverse events, serious adverse events and unanticipated problems will be made.

The above does not apply to those subjects who come off protocol specific treatment for unequivocal progression of disease. For this group, appropriate follow-up will continue for safety and survival as specified in the protocol.

All subjects who have received at least one dose of CC-122 and/or nivolumab will be included in the safety analysis. Subjects who withdraw during screening after being deemed eligible but have not started protocol specific therapy will be replaced. For patients to be included in the efficacy analysis, they should have received at least 75% of the cumulative dose of CC-122 during cycle 1. If this parameter is not met, they will be replaced after discussion with the study statistician.

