6.1.2 DURATION OF THERAPY

In the absence of progression or intolerable toxicity, therapy will continue up to a maximum of 52 weeks (13 cycles). For those patients who demonstrate continued improvement in radiographic response at scheduled restaging (anticipated around week 48) performed prior to reaching this landmark will be given the option of continuation of therapy. This provision is based on the recently reported analysis of advanced melanoma patients who achieved a complete response to pembrolizumab on KEYNOTE-001 where the median time to achieve CR was 12 months (range, 3-36).⁴⁴ For these subjects, therapy will continue for 1 cycle beyond CR (should they achieve this) or until 2 consecutive staging studies demonstrate a plateau in response. For those patients achieving CR as best response prior to 52 weeks, therapy can be discontinued provided they have completed at least 26 weeks of treatment.

If either CC-122 or nivolumab require discontinuation due to toxicity attributed exclusively to that agent (e.g., neutropenia secondary to CC-122), the second drug can continue for the duration as outlined above.

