- Obtain demographic information, medical history, and medication history.
- Record vital signs (including weight), results of examinations. Recording of height is necessary only
 at screening or baseline visit
- Collect study specific laboratory/biomarker tests and other studies that are outlined in the Schedule of Events. This also includes standard of care assessments.
- Administer the study treatment (nivolumab plus CC-122; first dose of CC-122 to be administered in the Clinical Research Unit).
- Collect blood for biomarker analysis at 5 hours post CC-122 administration.

Follow-up Visit (Visit 2; C1 Day 15; +/- 2 days)

- Record adverse events as reported by participant or observed by investigator.
- Record vital signs, confirm medical history and perform physical examination
- Collect blood for routine testing and biomarker analysis as specified.
- Administer nivolumab per institutional standard.
- Record participant's adherence to treatment program.
- Schedule/remind subject of follow-up tumor biopsy (same site as done at screening) to be done between days 22 and 29 of cycle 1.

Follow-up Visit (Visit 3; Cycle 2, day 1, +/- 2 days)

- Record adverse events as reported by participant or observed by investigator.
- Record vital signs, confirm medical history and perform physical examination
- Administer nivolumab and provide CC-122 for home use
- Record participant's adherence to treatment program.

Subsequent Visits to follow the 'Schedule of Events' calendar: All scheduled visits have the same window of +/- 2 days. If there is a need to schedule outside of this window, this may be done at the discretion of the principal investigator as long as there is no perceived jeopardy to the health of the participant. Tumor measurements by cross-sectional imaging will be performed every 12 weeks (+/- 7days) unless documented progression or subject taken off the clinical trial. Adverse events as reported by the subject or observed by the investigator will be recorded at each visit.

Final/End of Treatment (EOT) Study Visit

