- This should occur after the participant has completed all planned therapy or been discontinued from protocol therapy due to progression or toxicity. This visit should occur within 30 days of the last administered study drug or at the time of start of new anti-neoplastic therapy for melanoma, whichever is sooner. If study therapy related toxicity has not resolved by the date of this evaluation, follow up should continue till resolution of toxicity. Note that this is not necessary for toxicities that require long-term replacement therapy (e.g., thyroid replacement therapy, steroid replacement therapy, management of immune-mediated hyperglycemia).
- Record adverse events as reported by participant or observed by investigator.
- Record vital signs and physical examination
- Collect blood for EOT. Obtain biopsy of metastatic site if feasible, especially in case of progression to help inform mechanisms of resistance to anti-PD1 therapy.
- Record participant's adherence to treatment regimen.
- Subjects who discontinue trial treatment for a reason other than disease progression will
 move into the Follow-Up Phase and should be assessed every 12 weeks (± 7 days) by
 radiologic imaging to monitor disease status up to 24 months after the final patients is
 enrolled or until receiving treatment outside of this protocol. Every effort should be made to
 collect information regarding disease status until the start of new anti-neoplastic therapy,
 disease progression, death, or end of the study. Information regarding post-study antineoplastic treatment will be collected if new treatment is initiated.

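### The efficacy set is defined by cycle-1 CC-122 exposure and treated patients outside it are replaced; the available plan text pre-specifies no response rate in all treated patients to show what that selection does

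*Combined protocol and SAP*

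**What the plan says.** Section 5.4.1 sets two analysis populations. For safety, "All subjects who have received at least one dose of CC-122 and/or nivolumab will be included in the safety analysis". For efficacy, patients "to be included in the efficacy analysis, they should have received at least 75% of the cumulative dose of CC-122 during cycle 1". On those who fall short: "If this parameter is not met, they will be replaced after discussion with the study statistician". No criteria for that discussion are given, and no reason for the shortfall is exempted. The nearby sentence setting apart patients who come off for unequivocal progression precedes the replacement rule and concerns follow-up.

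Section 10.1 applies the Simon rules to 28 and then 41 evaluable patients in cohort 1, and to 16 and then 25 patients in cohort 2. It gives 66 (41 + 25) as the maximum enrolled. The stopping rules for toxicity in section 10.3 define a dose-limiting toxicity (DLT) as stopping one or both drugs for toxicity, and their boundary tables end at 41 and 25 patients.

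Two provisions bear on what data will exist. Section 5.4.1 says, if the subject agrees, "all efforts will be made to continue follow-up of withdrawn or terminated participants, especially for safety and efficacy end-points". Under section 7.1, patients who stop treatment for a reason other than progression "move into the Follow-Up Phase and should be assessed every 12 weeks (± 7 days) by" radiologic imaging.

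**The concern.** How much CC-122 a patient takes in cycle 1 is determined after treatment starts, partly by how the patient fares. Selecting on it in a single-arm trial, with no control arm subject to the same selection, can shift the objective response rate (ORR). The same event can count against the regimen for safety and disappear for efficacy: an early toxicity stop is a DLT but is absent from the ORR and from the stage 1 decision. Early death or clinical deterioration acts the same way, and those patients would be expected to respond less often.

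At stake are the primary endpoint in both cohorts and the futility look. If excluded patients do worse than those kept, the evaluable ORR flatters the regimen as given to all treated patients, and a cohort is less likely to stop early. If they do not, nothing is lost. A reader of the results would need an ORR in all treated patients to know which applies.

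**Working it through.** **Inputs from the documents.** Cohort 1: null 40%, alternative 60%, stop if 11 or fewer of 28 respond, reject at 21 or more of 41. Cohort 2: null 10%, alternative 30%, continue with 2 or more of 16, reject at 5 or more of 25 (section 10.1). CC-122: 2 mg, 5 days on and 2 off, 28-day cycle (6.1.1).

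**Assumptions.** The excluded share f and the response rate q among the excluded are not in the documents. I take f = 5% and 10% and vary q. I read 75% as a share of the planned cycle-1 dose.

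**Step 1: the plan's own figures.** P(reject) is the sum, over stage 1 counts x above the futility bound, of P(X1 = x) × P(X2 ≥ r − x), with exact binomials. Cohort 1: type I error 0.0951, power 0.9009. Cohort 2: 0.0951 and 0.9030. These match the 10% and 90% targets and the stated 9.5% and 90%. The chance of stopping at stage 1 under the null is 55.1% and 51.5%.

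**Step 2: who is excluded.** The planned cycle-1 dose is 20 × 2 mg = 40 mg, so the threshold is 30 mg, or 15 full doses. Dosing days are 1–5, 8–12, 15–19 and 22–26. A last dose on day 18 gives at most 14/20 = 70% (out); on day 19, 15/20 = 75% (in).

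**Step 3: error rate for all treated patients.** Hold the true ORR in all treated patients at the null p0. The rate among those kept is then (p0 − f·q)/(1 − f). Rerun the two-stage rule at that rate. For f = 10%:

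| Excluded respond at | Cohort 1: rate kept | Cohort 1: P(reject) | Cohort 2: rate kept | Cohort 2: P(reject) |
|---|---|---|---|---|
| 44% | 39.6% | 8.6% | – | – |
| null rate | 40.0% | 9.5% | 10.0% | 9.5% |
| 90% of null | 40.4% | 10.5% | 10.1% | 9.9% |
| 75% of null | 41.1% | 12.2% | 10.3% | 10.4% |
| 50% of null | 42.2% | 15.5% | 10.6% | 11.3% |
| never | 44.4% | 23.4% | 11.1% | 13.3% |

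The first row uses the nivolumab-alone figure in section 2.1 ("The response rates to treatment were 58%, 44% and 19% respectively", the middle value, in previously untreated patients): (0.40 − 0.10 × 0.44)/0.90 = 0.3956.

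For f = 5%, from the null rate down to never, P(reject) is 9.5/10.0/10.7/12.1/15.1% in cohort 1 and 9.5/9.7/9.9/10.4/11.2% in cohort 2.

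Mixed case in cohort 1, f = 10%: if 1 to 3 of the 10 percentage points never respond and the rest respond at 40%, P(reject) is 10.5% to 12.8%.

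**Step 4: the futility look.** At f = 10% and half the null rate, the chance of stopping at stage 1 falls from 55.1% to 45.5% in cohort 1 and from 51.5% to 48.5% in cohort 2.

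**Step 5: enrolment.** Filling the slots takes on average 41/(1 − f) and 25/(1 − f) treated patients: 43.2 and 26.3 at 5%, 45.6 and 27.8 at 10%. At full accrual any replaced treated patient takes the dosed total above 66 and beyond the last entry of that cohort's toxicity table. That 41 counts evaluable patients is explicit; that 25 does is inferred from 5.4.1.

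**The case against.** The strongest reply is that the design does what it says. Cohort 1 is sized on evaluable patients, 5.4.1 defines the efficacy set, and in that set the error rates are right. An evaluable set is also a defensible choice for a phase II activity question. This stands. A reader might infer that the trial's type I error is wrong; the documents do not support that. Inflation arises only for a null about all treated patients, under an assumed excluded share and response rate.

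A reader might also infer that any bias would be hidden for good. That does not follow either: continued efficacy follow-up and 12-weekly imaging mean the data should largely exist. Nor can one say that the plan has no such analysis anywhere. The contents list a section 10.4.1, Exploratory Analyses, whose text is not in the available copy.

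Other points narrow the effect:

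- A 7-day hold within cycle 1 misses 5 of 20 doses, so resuming at the same dose leaves exactly 75% and the patient stays in.
- Routine scans are 12-weekly and so would not find progression in cycle 1. Section 10.3 also lets clinically stable patients continue after initial radiographic progression.
- Where toxicity is exclusive to CC-122, "the second drug can continue for the duration as outlined above" (6.1.2), so in cohort 1 those patients may respond about as often as the null rate assumes.
- Replacement follows a discussion with the statistician and is not described as automatic.

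These reduce the likely size without removing the route. Where toxicity is not clearly exclusive to one drug, 6.1.3 delays both by default, and early clinical progression or death still excludes. The discussion has no stated criteria.

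**Conclusion.** The point holds in limited form. The efficacy set is selected on a post-treatment outcome, treated patients outside it are to be replaced without stated criteria, and nothing in the available text of section 10 would show the effect.

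The direction and size are not known. With an assumed 10% excluded, the error rate for all treated patients runs from 8.6% to 23.4% in cohort 1 and from 9.5% to 13.3% in cohort 2. The upper ends require that no excluded patient responds. Values toward the lower end are plausible if exclusions are mostly for CC-122 toxicity with nivolumab continuing. The effect in cohort 2 is small throughout.

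The mismatch between replacement, the maximum of 66 and the toxicity tables needs no assumption about response, only that at least one treated patient is replaced in a cohort that accrues fully. It should be fixed because the remedy is cheap; no material bias has been shown.

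**What to change.** In 5.4.1 and 10.1, keep the 75%-dose set for the Simon rules if wished, and add:

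1. At both stages, a pre-specified ORR in all patients with at least one dose (the set 5.4.1 already uses for safety), counting those without a post-baseline response assessment as non-responders.
2. The number of exclusions and replacements, with reasons, and the criteria for the discussion with the statistician.
3. A reconciliation of the maximum of 66, and of the toxicity boundaries ending at 41 and 25, with the replacement of treated patients.

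The cost is slightly more analysis and a second ORR that may be less favourable. Power in the evaluable set is unchanged.

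Making the all-treated set primary, and replacing only patients never dosed, would leave the boundaries, totals and tables as written, but it is a trade-off for the sponsor to weigh. Suppose the alternative rates hold only in adequately dosed patients and 10% of treated patients fall outside. If those 10% never respond, the all-treated rates are 0.9 × 60% = 54% and 0.9 × 30% = 27%, and power is 69% and 84%. If they respond at the null rates, the all-treated rates are 54% + 0.1 × 40% = 58% and 27% + 0.1 × 10% = 28%, and power is 85% and 86%.
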